12.10. Appendix 10: Protocol Amendment History

Not applicable

**Description:**

- The purpose of this RAP is to describe the planned analyses and output to be included in the Clinical Study Report for Protocol 205037.
- This RAP is intended to describe the final analyses required for the study.
- This RAP will be provided to the study team members to convey the content of the Statistical Analysis Complete (SAC) deliverable.

## 1. INTRODUCTION

The purpose of this reporting and analysis plan (RAP) is to describe the analyses to be included in the Clinical Study Report for Protocol: 205037

## 2. SUMMARY OF KEY PROTOCOL INFORMATION

### 2.1. Changes to the Protocol Defined Statistical Analysis Plan

There were no changes or deviations to the originally planned statistical analysis specified in the protocol (Dated: 07/JUN/2018).

### 2.2. Study Objective(s) and Endpoint(s)

Objectives	Endpoints

To assess the safety and tolerability of TID doses for one day of GSK2982772 in Japanese healthy male subjects.

To characterise the PK profile of TID doses for one day of GSK2982772 in Japanese healthy male subjects.

	

Adverse events (AEs)

Change in laboratory values (clinical chemistry, haematology and urinalysis), 12-lead ECG, vital signs (blood pressure, pulse rate, and body temperature)

Physical examinations, including neurological examinations.

Derived PK parameters for GSK2982772, including area under the plasma drug concentration versus time curve over 24 hr (AUC(0-24)) and AUC over each dose interval (i.e. AUC(0-7), AUC(7-14) and AUC(14-24)). Maximum observed plasma drug concentration (Cmax) following each dose, time to maximum observed plasma drug concentration (Tmax) following each dose, terminal half-life (t1/2) following the third dose, observed trough plasma drug concentrations (C0, C7, C14 and C24), where data allow

## 2.3. Study Design

Overview of Study Design and Key Features																																			

  
 Group	N	Period 1	Period 2	Period 3	Period 4	
   
 A	3	Placebo, TID	60 mg, TID	120 mg, TID	240 mg, TID	
 
 B	3	60 mg, TID	Placebo, TID	120 mg, TID	240 mg, TID	
 
 C	3	60 mg, TID	120 mg, TID	Placebo, TID	240 mg, TID	
 
 D	3	60 mg, TID	120 mg, TID	240 mg, TID	Placebo, TID	
  
						Group	N	Period 1	Period 2	Period 3	Period 4	A	3	Placebo, TID	60 mg, TID	120 mg, TID	240 mg, TID	B	3	60 mg, TID	Placebo, TID	120 mg, TID	240 mg, TID	C	3	60 mg, TID	120 mg, TID	Placebo, TID	240 mg, TID	D	3	60 mg, TID	120 mg, TID	240 mg, TID	Placebo, TID
Group	N	Period 1	Period 2	Period 3	Period 4																														
A	3	Placebo, TID	60 mg, TID	120 mg, TID	240 mg, TID																														
B	3	60 mg, TID	Placebo, TID	120 mg, TID	240 mg, TID																														
C	3	60 mg, TID	120 mg, TID	Placebo, TID	240 mg, TID																														
D	3	60 mg, TID	120 mg, TID	240 mg, TID	Placebo, TID																														

 
 Screening	Within 30 days prior to the first dosing.	
 
 Treatment Period	The study will be comprised of four study periods each at least 7 days in duration with subjects in-house for 4 nights (through 72 hours after the 1st dose). During each treatment period, subjects will be admitted to the unit the day before dosing and will be discharged after completion of the 72-hour post-dose assessments. Each subject will receive oral TID doses of GSK2982772 in fasted condition in each treatment period. For TID dosing, GSK2982772 or placebo will be administered using a 7 hr, 7 hr dosing interval.	
 
 Washout Period	Will be at least 7 days between treatment period doses for an individual subject.	
 
 Follow-up	At least 7 days, and no greater than 14 days after last study treatment administration. If warranted, additional follow-up visits may be scheduled.	
 
						Screening	Within 30 days prior to the first dosing.	Treatment Period	The study will be comprised of four study periods each at least 7 days in duration with subjects in-house for 4 nights (through 72 hours after the 1st dose). During each treatment period, subjects will be admitted to the unit the day before dosing and will be discharged after completion of the 72-hour post-dose assessments. Each subject will receive oral TID doses of GSK2982772 in fasted condition in each treatment period. For TID dosing, GSK2982772 or placebo will be administered using a 7 hr, 7 hr dosing interval.	Washout Period	Will be at least 7 days between treatment period doses for an individual subject.	Follow-up	At least 7 days, and no greater than 14 days after last study treatment administration. If warranted, additional follow-up visits may be scheduled.																						
Screening	Within 30 days prior to the first dosing.																																		
Treatment Period	The study will be comprised of four study periods each at least 7 days in duration with subjects in-house for 4 nights (through 72 hours after the 1st dose). During each treatment period, subjects will be admitted to the unit the day before dosing and will be discharged after completion of the 72-hour post-dose assessments. Each subject will receive oral TID doses of GSK2982772 in fasted condition in each treatment period. For TID dosing, GSK2982772 or placebo will be administered using a 7 hr, 7 hr dosing interval.																																		
Washout Period	Will be at least 7 days between treatment period doses for an individual subject.																																		
Follow-up	At least 7 days, and no greater than 14 days after last study treatment administration. If warranted, additional follow-up visits may be scheduled.																																		
Design Features	
 
This study will be a double-blind with respect to subjects, investigator and site staff (with the exception of the unblinded site pharmacist), a three times daily/day, ascending dose, randomized, placebo-controlled, 4-way crossover study.
 
																																		
Dosing	
 
The initial starting dose planned is 60 mg TID and the maximum dose is 720 mg/day administered as 240 mg TID, which cover the dose range of the proposed Ph2b study.
 
Sentinel dosing will be employed within each dosing period of the study. The doses in the single-ascending dose portion of the study will be staggered such that for each dose, on Day 1, two of the 12 subjects will be randomized to treatment (one subject will receive GSK2982772 and one subject will receive matched-placebo). Assuming 2 subjects are dosed on Day 1 and assuming adequate safety (AEs, clinical labs, vital signs and ECGs) in the judgment of the principal investigator and GSK Medical Monitor through approximately 24 hours after their 2nd dose on Day 1, the remaining subjects may be randomized to dosing in that period.
 
60 mg, 120 mg, and 240 mg of GSK2982772 will be administered in each sentinel dosing which occurred on Period 1, 2, and 3, respectively.
 
																																		
Time & Events	
 
Refer to Appendix 2: Schedule of Activities
 
																																		
Treatment Assignment	
 
On Day 1, participants will be assigned a unique number (randomization number) in ascending numerical order. The randomization number encodes the participant's assignment to one of the 4 groups, according to the randomization schedule generated prior to the study by the Biomedical Data Sciences Department at GSK. Each participant will be dispensed blinded study treatment, labelled with his unique randomization number, throughout the study.
 
Subjects will be randomized to one of four sequences (A, B, C, and D), where the treatments in the sequences are:
 
																																		

Overview of Study Design and Key Features	
	

 A: Placebo TID / 60 mg TID / 120 mg TID / 240 mg TID

 B: 60 mg TID / Placebo TID / 120 mg TID / 240 mg TID

 C: 60 mg TID / 120 mg TID / Placebo TID / 240 mg TID

 D: 60 mg TID / 120 mg TID / 240 mg TID / Placebo TID

Interim Analysis	

• No interim analysis is planned.

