7.2. Method of Treatment Assignment

On Day 1, participants will be assigned a unique number (randomization number) in ascending numerical order. The randomization number encodes the participant's assignment to one of the 4 groups, according to the randomization schedule generated prior to the study by the Biomedical Data Sciences Department at GSK. Each participant will be dispensed blinded study treatment, labelled with his unique randomization number, throughout the study.

Subjects will be randomized to one of four sequences (A, B, C and D), where the treatments in the sequences are:

- A: Placebo TID / 60 mg TID / 120 mg TID / 240 mg TID
- B: 60 mg TID / Placebo TID / 120 mg TID / 240 mg TID
- C: 60 mg TID / 120 mg TID / Placebo TID / 240 mg TID
- D: 60 mg TID / 120 mg TID / 240 mg TID / Placebo TID

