5.3. Sentinel Dosing

The doses will be staggered such that for each dose, on Day 1 of Period 1, 2 and 3, two of the 12 subjects will be randomized to treatment (one subject will receive GSK2982772 and one subject will receive matched-placebo). Assuming 2 subjects are dosed on Day 1 and assuming adequate safety (AEs, clinical labs, vital signs, 12-Lead ECGs and findings during continuous cardiac telemetry) in the blind judgment of the principal investigator

and GSK Medical Monitor through at least 24 hrs after their third dose on Day 1, the remaining subjects may be randomized to dosing in that period.

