7.3. Blinding

This study will be a double-blind with respect to subjects, investigators and site staff (with the exception of the unblinded site pharmacist).

Investigators will remain blinded to each participant's assigned study treatment throughout the course of the study.

A participant will be withdrawn if the participant's treatment code is unblinded. The primary reason for discontinuation (the event or condition which led to the unblinding) will be recorded in the case report form (CRF).

GSK's Global Clinical Safety and Pharmacovigilance (GCSP) staff may unblind the treatment assignment for any participant with an SAE. If the SAE requires that an expedited regulatory report be sent to one or more regulatory agencies, a copy of the report, identifying the participant's treatment assignment, may be sent to principal investigator in accordance with local regulations and/or GSK policy.

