- An event is defined as 'serious' when it meets at least 1 of the predefined outcomes as described in the definition of an SAE, NOT when it is rated as severe.

Assessment of Causality

- The investigator is obligated to assess the relationship between study treatment and each occurrence of each AE/SAE.
- A "reasonable possibility" of a relationship conveys that there are facts, evidence, and/or arguments to suggest a causal relationship, rather than a relationship cannot be ruled out.
- The investigator will use clinical judgment to determine the relationship.
- Alternative causes, such as underlying disease(s), concomitant therapy, and other risk factors, as well as the temporal relationship of the event to study treatment administration will be considered and investigated.
- The investigator will also consult the IB and/or Product Information, for marketed products, in his/her assessment.
- For each AE/SAE, the investigator **must** document in the medical notes that he/she has reviewed the AE/SAE and has provided an assessment of causality.
- There may be situations in which an SAE has occurred and the investigator has minimal information to include in the initial report to GSK. However, **it is very important that the investigator always make an assessment of causality for every event before the initial transmission of the SAE data to GSK.**
- The investigator may change his/her opinion of causality in light of follow-up information and send an SAE follow-up report with the updated causality assessment.
- The causality assessment is one of the criteria used when determining regulatory reporting requirements.

Follow-up of AE and SAE

- The investigator is obligated to perform or arrange for the conduct of supplemental measurements and/or evaluations as medically indicated or as requested by GSK to elucidate the nature and/or causality of the AE or SAE as fully as possible. This may include additional laboratory tests or investigations, histopathological examinations, or consultation with other health care professionals.
- If a participant dies during participation in the study or during a recognized follow-up period, the investigator will provide GSK with a copy of any post-mortem findings including histopathology.
- New or updated information will be recorded in the originally completed CRF.
- The investigator will submit any updated SAE data to GSK within 24 hrs of receipt of the information.

Reporting of SAE to GSK

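### Naming the Period 2 and 3 sentinels reveals those men's earlier treatments, and re-using a sentinel would reveal his former partner's whole sequence, so the blinding stated in Protocol 7.3 is not achieved

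*SAP*

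**What the plan says.** Protocol 7.2 fixes each man's whole course with one randomization number, using four sequences of three men. The first begins on placebo: "A: Placebo TID / 60 mg TID / 120 mg TID / 240 mg TID". In the other three, the placebo day moves to Period 2 (B), Period 3 (C) or Period 4 (D), and the three active doses are taken in ascending order in the periods that are left.

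Protocol 5.3 has a sentinel pair in each of Periods 1, 2 and 3, in which "one subject will receive GSK2982772 and one subject will receive matched-placebo". The principal investigator and the medical monitor judge the pair's safety before the other men are dosed. SAP 2.3 supplies the active doses: "60 mg, 120 mg, and 240 mg of GSK2982772 will be administered in each sentinel dosing which occurred on Period 1, 2, and 3".

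Protocol 7.3 states: "Investigators will remain blinded to each participant's assigned study treatment throughout the course of the study". Protocol 5.4 also describes the escalation data as blind. Neither document says how the Period 2 and 3 sentinels are chosen or whether a man may serve twice, and neither acknowledges that the choice carries information.

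**The concern.** The sentinels cannot be hidden from the site, because they are dosed ahead of the rest and reviewed by name. The sequences are fixed and printed in the protocol. Eligibility to be a sentinel in a later period therefore depends on what a man received earlier, and naming him discloses it.

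At stake are the investigator's judgements of AE intensity and causality. These feed the halting rules in Protocol 8.1.1 (for example, two men with the same moderate AE judged related) and the drug-related AE tables (SAP Tables 2.3 and 2.4). With 12 men per treatment, one reclassified event moves a rate by 1/12 = 8.3 percentage points. Comparison with placebo rests on descriptive summaries alone (Protocol 10.4.1), so the blind is the main protection for those tables.

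**Working it through.** **Inputs.** Sequences: Protocol 7.2. Three men per sequence, 12 in all: Protocol 10.1. Pair composition: Protocol 5.3. Sentinel active doses: SAP 2.3.

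**Step 1: reproduce the plan's own count.** Men per treatment and period:

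| | P1 | P2 | P3 | P4 | Total |
|---|---|---|---|---|---|
| Placebo | 3 | 3 | 3 | 3 | 12 |
| 60 mg | 9 | 3 | 0 | 0 | 12 |
| 120 mg | 0 | 6 | 6 | 0 | 12 |
| 240 mg | 0 | 0 | 3 | 9 | 12 |

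This matches the 12 per treatment in Protocol 10.1. The six men on 120 mg in Period 2 meet the minimum of six in Protocol 5.4.

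**Step 2: who can be a sentinel.**

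| Period | Active sentinel | Placebo sentinel | Earlier treatment of both |
|---|---|---|---|
| 1 (60 mg) | B, C or D | A | none |
| 2 (120 mg) | C or D | B | 60 mg |
| 3 (240 mg) | D | C | 60 mg, then 120 mg |

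**Step 3: six different sentinels.** Each Period 2 sentinel reveals one earlier period and each Period 3 sentinel reveals two: 2×1 + 2×2 = 6 of 12×4 = 48 man-periods (four at 60 mg, two at 120 mg). Before naming, the chance of 60 mg in Period 1 was 9/12 = 75%, and of 120 mg in Period 2 was 6/12 = 50%; afterwards both are 100%. Which man of the current pair has placebo stays 50/50. The Period 3 sentinels are C or D with equal chance, so their chance of placebo in Period 4 is 50% instead of 3/12 = 25%.

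**Step 4: one sentinel re-used.** Possible pairs (active × placebo) number 9×3 = 27 in Period 1, 6×3 = 18 in Period 2 and 3×3 = 9 in Period 3.

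- Periods 1 and 2: 27×18 = 486 combinations. Of these, 378 share no man, 108 share one and 0 share both. In all 108 the Period 1 partner is A.
- Periods 1 and 3: 54 of 27×9 = 243 share one man and 0 share both. In all 54 the Period 1 partner is A.
- Periods 2 and 3: 18×9 = 162 combinations. Of these, 108 share none, 54 share one and 0 share both. In all 54 the Period 2 partner is B.

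The reason is that A cannot be a sentinel after Period 1, and B cannot be one after Period 2. A man who returns must have been the active one, so his partner had placebo.

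**Step 5: certain man-periods by pattern**, with a pair in all three periods:

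| Pattern | Sum over men | Total of 48 | Fully identified | Known before given |
|---|---|---|---|---|
| Six different men | 1+1+2+2 | 6 | none | 0 |
| One man in P2 and P3 | 2+4+2 | 8 | one B | 2 |
| One man in P1 and P2, new P3 pair | 1+4+1+2+2 | 10 | one A | 3 |
| One man in P1 and P3 | 2+4+1+1+2 | 10 | one A | 2 |
| One man in all three | 2+4+4+2 | 12 | one A, one B | 3+2 = 5 |

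**Step 6: effect on escalation.** The move to 120 mg is decided on Period 1 data, before a second pair is named. The move to 240 mg rests on 120 mg in Period 2, which only C and D men receive. An identified A man has 60 mg in Period 2 and 120 mg in Period 3, and an identified B man has 120 mg in Period 3. Neither is on the newly reached dose in those periods.

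**The case against.** The case against is strongest on consequence.

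- **The certain leak is retrospective and small.** It is 6 man-periods, each already 75% likely to be active (9/12), and the end-of-period review (Protocol 5.4 and 10.4.3) normally comes before the next pair is named. This stands. Past-period disclosure does harm only if assessments are completed or changed afterwards.
- **Late revision is weakly documented.** A reader might cite "The investigator may change his/her opinion of causality in light of follow-up information" (Protocol Appendix 4) as a general licence to re-rate past AEs. That sentence goes on to SAE follow-up reports, so it does not support this for non-serious events. Equally, nothing requires non-serious AEs to be finalised by any date.
- **Re-use is hypothetical.** The documents do not plan it, and the Study Reference Manual, which is not available here, may contain a rule. This stands as a limit on likelihood. A safeguard for the blind should still be in the protocol.
- **The direction of bias is not fixed.** A reader might infer that only active periods are revealed, so that bias always runs towards calling events drug-related. That holds for six different sentinels only. Under re-use the partner's placebo period is revealed as well.
- **Measured endpoints are unaffected.** PK, laboratory, ECG and vital-sign values do not depend on causality, no hypothesis is tested, and the all-AE table needs no relatedness judgement. This stands.

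**Conclusion.** The contradiction is real: the sentinel scheme cannot deliver the blinding that Protocol 7.3 states. With men randomized at the start, every choice of sentinels discloses something, because each later pair is either all new or shares one man with an earlier pair. The size is 6 of 48 man-periods (12.5%) with six different sentinels and 8 to 12 (up to 25%) with re-use. Only re-use gives certain knowledge of a treatment before it is given, for one or two men.

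A reader might go further and infer that the current sentinel's treatment is known, or that the escalation decisions are unblinded. The documents support neither: the current pair stays 50/50, and next-level data come from C and D men. A general halt of dosing could still be touched by an identified man's events.

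Assumptions: the investigator knows the sequence table and who the sentinels are, as the protocol implies; the SAP sentinel doses apply (the protocol alone is less explicit, and certainty rests on the SAP sentence); and no sentinel is a replacement who starts in that period, since such a man has no earlier treatment to reveal and the count would be lower.

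**What to change.** 1. In Protocol 5.3, mirrored in SAP 2.3, state that no subject is a sentinel in more than one period, and that unblinded staff (the site pharmacist or an unblinded statistician) pick the sentinels from the schedule. This removes the only route to certain advance knowledge.
2. Require intensity and causality of all AEs in a period to be entered and signed before the next period's sentinels are named, with any later change flagged in SAP Listing 14.
3. Amend Protocol 7.3 to say that the earlier-period treatment of the Period 2 and 3 sentinels is deducible.

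This costs two or three sentences and changes no dose, sequence or sample size. Since a pair can never repeat, at least one new man is needed each time anyway, and using two adds little or no delay. Sign-off fits the existing end-of-period safety review. The downside is earlier AE sign-off at the site. The 6 man-period retrospective leak is limited in effect, not removed.

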## **2.4. Statistical Hypotheses / Statistical Analyses**

The objectives of this study are to evaluate safety, tolerability and pharmacokinetics of GSK2982772 in healthy Japanese subjects. No formal statistical hypotheses will be tested. Descriptive statistics will be used to assess safety and tolerability. An estimation approach will be used to address the pharmacokinetic study objectives, where point estimates and corresponding confidence intervals will be constructed.

### 3. PLANNED ANALYSES

#### 3.1. Interim Analyses

A review of safety data will be conducted at the end of each period.

The decision to proceed to higher dose strengths will be made by principal investigator and GSK's Medical Monitor based on assessment of safety and tolerability at the preceding dose. This review can include individual subject data.

#### 3.2. Final Analyses

The final planned primary analyses will be performed after the completion of the following sequential steps:

1. All participants have completed the study as defined in the protocol.
2. All required database cleaning activities have been completed and final database release (DBR) and database freeze (DBF) has been declared by Data Management.
3. All criteria for unblinding the randomization codes have been met.
4. Randomization codes have been distributed according to RandAll NG procedures.

### 4. ANALYSIS POPULATIONS

Population	Definition / Criteria	Analyses Evaluated
Screened	

• All subjects who have a screening visit will be included

	

• Study Population

Enrolled	

• All subjects who passed screening and enter the study will be included.

• Note screening failures (who never passed screening even if rescreened) and subjects screened but never enrolled into the study (Reserve, Not Used) are excluded from the Enrolled population as they did not enter the study.

	

• Study Population

Safety	

• All subjects who have received at least one dose of study treatment will be included.

	

• Study Population

• Safety

Pharmacokinetic (PK)	

• All subjects in the Safety population for whom a pharmacokinetic sample has been obtained and analyzed will be included.

	

• PK

Refer to [Appendix 9](#): List of Data Displays which details the population used for each display.

#### **4.1. Protocol Deviations**

Important protocol deviations (including deviations related to study inclusion/exclusion criteria, conduct of the trial, patient management or patient assessment) will be summarised and listed.

Protocol deviations will be tracked by the study team throughout the conduct of the study in accordance with the Protocol Deviation Management Plan.

- Data will be reviewed prior to freezing the database to ensure all important deviations are captured and categorised on the protocol deviations dataset.
- This dataset will be the basis for the summaries and listings of protocol deviations.

A separate summary and listing of all inclusion/exclusion criteria deviations will also be provided. This summary will be based on data as recorded on the inclusion/exclusion page of the eCRF.

